**Research on the Construction of a Prognostic Model for COPD
Complicated with Sarcopenic Obesity Based on Bioelectrical
Impedance Phase Angle Technology (COSAT)**

Research Protocol

Main researchers: [name], [name]

Clinical research department: Respiratory and Critical Care

Medicine Sponsor: [name]

Ethics Review No.:2025K200

Scheme Version No: 01

Plan Preparation date: July 15th, 2025

Research Objectives:

This study aims to explore the diagnosis, impact, and prognostic factors of COPD complicated with sarcopenic obesity using multi-segment bioelectrical impedance phase angle technology. It seeks to clarify the diagnostic value and efficacy of body composition analysis in specific populations, analyze the relationship between phase angle and COPD severity as well as quality of life, investigate its predictive role for adverse outcomes, and reveal the effects of inflammation and metabolic disorders in sarcopenic obesity. The goal is to provide a basis for early screening and precise intervention to improve patient prognosis.

Proposed Research Methods

Inclusion Criteria

- (1) Age over 65 years;**
- (2) Ability to complete physical activity assessments and pulmonary function tests;**
- (3) Complete medical records, willingness to adhere to follow-up arrangements, and provision of adverse event reports via telephone or outpatient visits, with signed informed consent;**
- (4) COPD diagnosis based on the American Thoracic Society (ATS)/European Respiratory Society (ERS) GOLD definition, with a post-bronchodilator FEV1/FVC ratio < 0.70, current or former smokers with a smoking history of ≥ 10 pack-years.**

Exclusion Criteria:

- (1) Severe cognitive impairment or hand deformities (e.g., rheumatoid arthritis) preventing body composition measurements;**
- (2) Incomplete clinical or follow-up data or unwillingness/inability to undergo regular follow-up;**
- (3) Severe systemic edema;**
- (4) Presence of cardiac pacemakers or significant metal implants that may interfere with measurements;**
- (5) Voluntary withdrawal for any reason, including loss to follow-up.**

Data Collection:

Demographic and clinical data: Gender, smoking status (never, former, current), age, height, weight, waist circumference, BMI, skeletal muscle index (SMI), body fat content,

visceral fat index, and segmental phase angles measured via bioelectrical impedance analysis.

Clinical records: Smoking history, comorbidities (Charlson Comorbidity Index), nutritional status (MNA-SF), physical performance (SPPB), medication use, pulmonary function tests, COPD exacerbations in the past year, CAT score, mMRC score, and St. George's Respiratory Questionnaire (SGRQ).

Laboratory tests: Blood samples for CBC, CRP, cholesterol, albumin, HbA1c, IL-6, and TNF- α (ELISA).

Sample Size Calculation:

Using PASS 15.0 for repeated-measures ANOVA ($\alpha = 0.05$, power = 90%), with a COPD prevalence of 15% and a 2:1 ratio for sarcopenic obesity vs. non-sarcopenic groups, the study requires 200 participants (33 sarcopenic obese, 33 non-obese sarcopenic, 72 obese non-sarcopenic, and 72 non-obese non-sarcopenic).

Diagnostic Criteria:

Sarcopenia: Asian Working Group criteria: SMI (InBody S10) $<7.0 \text{ kg/m}^2$ (men) or $<5.7 \text{ kg/m}^2$ (women); grip strength $<28 \text{ kg}$ (men) or $<18 \text{ kg}$ (women); gait speed $<0.8 \text{ m/s}$. **Obesity:** BMI $\geq 28 \text{ kg/m}^2$ or waist circumference $\geq 85 \text{ cm}$ (men)/ $\geq 80 \text{ cm}$ (women); body fat $\geq 24.3\%$ (men) or $\geq 33.2\%$ (women).

sarcopenic Obesity: Coexistence of sarcopenia and obesity.

Assessments:

Physical Performance: Short Physical Performance Battery (SPPB: balance, gait speed, chair stands; score 0–12).

Nutritional Status: Mini Nutritional Assessment (MNA-SF; score 0–12).

Phase Angle: Measured via InBody S10 at six frequencies (1kHz–1000kHz) across five body segments, calculated using resistance (R) and reactance (Xc):

$\text{PHA} = \arctan((\text{Xc_right arm} + \text{Xc_trunk} + \text{Xc_right leg}) / (\text{R_right arm} + \text{R_trunk} + \text{R_right leg})) \times 180^\circ / \pi$.

Follow-up Endpoints:

Primary: Changes in pulmonary function, dyspnea scores, and body composition at 2 years.

Secondary: Acute exacerbations, hospitalizations, or death within 2 years. Follow-ups at 6, 12, and 24 months.

Grouping patients based on whether they have sarcopenic obesity, the differences in clinical data between the two groups were analyzed. Statistical analysis was performed using SPSS 24.0 statistical software.

Analysis of Demographic Characteristics and Clinical Data:

The age and gender distribution of the patients were described. Based on whether the patients had sarcopenic obesity, they were divided into two groups. The differences in clinical data between the two groups, including age distribution, smoking status, obesity-related body fat, pulmonary function, whole-body and segmental phase angle, were analyzed. Continuous variables were expressed as mean \pm standard deviation, and categorical variables were expressed as percentages. Differences between groups were analyzed using Student's t-test for continuous variables and the chi-square test for categorical variables, depending on the data type.

Analysis of Factors Associated with COPD Complicated by Sarcopenic Obesity:

Univariate and multivariate analyses were conducted on data from COPD patients with sarcopenic obesity. Using clinical data variables, nutritional status, physical activity capacity, whole-body and segmental phase angle, logistic regression was applied to analyze the factors associated with sarcopenic obesity in COPD patients.

Analysis of the Prognostic Predictive Value of Sarcopenic Obesity in Obstructive Pulmonary Disease:

The differences in hospital stay length, acute exacerbation readmission rate, and mortality between COPD patients with sarcopenic obesity and those without sarcopenia at baseline were compared. Kaplan-Meier analysis was used for statistical analysis, and differences were expressed using the log-rank test.

COSAT study

INFORMED CONSENT FORM

This document provides you with information to help you decide whether to participate in this clinical research study. Please read it carefully. If you have any questions, please direct them to the researcher in charge of this study.

Your participation in this study is voluntary. This research has been reviewed and approved by the institutional ethics review committee of our research institution.

The background, objectives, research process, and other important information are as follows:

Research Purpose:

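### The plan promises the diagnostic value of body composition analysis, phase angle included, but schedules no analysis that estimates diagnostic accuracy

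*Combined protocol and SAP*

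**What the plan says.** The Research Objectives set out to study the diagnosis, impact and prognosis of COPD with sarcopenic obesity "using multi-segment bioelectrical impedance phase angle technology". The next sentence gives the objective at issue: "It seeks to clarify the diagnostic value and efficacy of body composition analysis in specific populations". The section ends with the intended use: "The goal is to provide a basis for early screening and precise intervention to improve patient prognosis".

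Three analyses are described.

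- *Analysis of Demographic Characteristics and Clinical Data* splits patients by sarcopenic-obesity status and compares a list of variables ending in "pulmonary function, whole-body and segmental phase angle, were analyzed". The method: "Differences between groups were analyzed using Student's t-test for continuous variables and the chi-square test for categorical variables".
- *Analysis of Factors Associated with COPD Complicated by Sarcopenic Obesity* enters clinical variables, nutritional status, physical capacity and phase angle in univariate and multivariate models: "logistic regression was applied to analyze the factors associated with sarcopenic obesity in COPD patients".
- The prognostic analysis compares outcomes by baseline group: "Kaplan-Meier analysis was used for statistical analysis, and differences were expressed using the log-rank test". It does not assess phase angle as a test for the condition.

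The analysis text plans no ROC curve, AUC, sensitivity, specificity, predictive value, cut-off for phase angle, or validation. It gives no criterion for calling a measure diagnostically valuable.

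**The concern.** A t-test asks whether two group means differ. A logistic regression for associated factors asks whether the odds of the condition vary with the marker. A diagnostic objective asks how well the marker sorts individual patients. With enough patients, a difference in means can be significant while the two distributions overlap almost completely.

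As written, then, the plan produces no number that answers its diagnostic objective. A statement about screening would have to lean on a p-value or an odds ratio, or on a cut-off improvised after the data are seen. Nothing planned would show a reader that a significant marker discriminates poorly.

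**Working it through.** **Inputs.** From Sample Size Calculation: alpha 0.05, power 90%, stated total 200, groups of 33, 33, 72 and 72. Sidedness is not stated; two-sided is assumed. The documents give no mean, SD or expected difference for phase angle. Normality and equal variance are therefore assumed, and the results are illustrations.

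**The plan's own figures.** There is no accuracy figure to reproduce. The groups sum to 33 + 33 + 72 + 72 = 210, not 200, so both totals are carried. The comparison group is 200 − 33 = 167 or 210 − 33 = 177. The repeated-measures ANOVA calculation cannot be rerun, because no effect size, SD or correlation is given.

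**Smallest significant difference.** d = t(0.975) × √(1/n₁ + 1/n₂) = t(0.975) / k, with k = √(n₁n₂/(n₁ + n₂)).

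- 33 v 177: k = √(33 × 177/210) = 5.274; d = 1.971/5.274 = 0.374.
- 33 v 167: d = 0.376.

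**Translation to accuracy.** Under the assumptions, AUC = Φ(d/√2), and at the midpoint cut-off sensitivity = specificity = Φ(d/2). The 90% power row uses d = 3.2415/k.

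| Difference | n | d | AUC | Sens. = spec. |
|---|---|---|---|---|
| Just significant | 33 v 177 | 0.374 | 0.604 | 57.4% |
| Just significant | 33 v 167 | 0.376 | 0.605 | 57.4% |
| 90% power | 33 v 177 | 0.615 | 0.668 | 62.1% |
| 90% power | 33 v 167 | 0.618 | 0.669 | 62.1% |

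On the logistic scale, d = 0.376 is an odds ratio of exp(0.376) ≈ 1.46 per SD. The choice between 200 and 210 makes no practical difference.

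**Precision if accuracy were reported.** Hanley-McNeil at AUC 0.75 with 33 v 177: SE = 0.0516, half-width 1.96 × 0.0516 = 0.101. Approximate 95% intervals at other values are 0.49 to 0.71 for AUC 0.60, 0.59 to 0.81 for 0.70, and 0.71 to 0.89 for 0.80. A sensitivity of 26/33 = 79% has an exact 95% interval of 61% to 91%. Splitting the cases by sex widens this: 12/16 gives 48% to 93%, and 6/8 gives 35% to 97%. The expected sex split is not stated.

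**The case against.** Several points on the other side have force.

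*The objective names body composition analysis, not phase angle.* Correct. Phase angle comes in from the preceding sentence, where it is the technology used to explore diagnosis, and from the analysis text. That is a reading, though a natural one. The other body composition measures, such as skeletal muscle index and body fat, help to define the condition, so their accuracy against it would be partly circular.

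*Nothing says that significance will be read as diagnostic value.* This stands. A reader might infer that a weak marker would be declared useful, but the plan contains no decision rule. It only leaves that possibility open.

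*The multivariate model already shows what phase angle adds.* This stands in part. Age is among the clinical data and gender is collected, so an adjusted coefficient can test an independent association. It does not give the gain in discrimination. A logistic model could also yield an AUC, but none is planned, and a model with many variables would not isolate phase angle.

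*AUC 0.60 is a boundary case.* This also stands. It is the weakest result that reaches significance, and it shows what is possible. A reader might infer that phase angle is expected to perform this poorly, but the documents give no basis for any expected value. Predictive values are left out of the argument for a similar reason: the group sizes are sample-size figures, not a prevalence estimate. With sensitivity and specificity at 57%, the positive predictive value runs from 7% at 5% prevalence to 37% at 30%.

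*An AUC would have its own problem.* Diagnostic Criteria take skeletal muscle index from the InBody S10, and Assessments take phase angle from the same device. Accuracy against that label may be inflated, and bootstrap correction does not remove this. It limits how an accuracy estimate can be read, but it does not turn a t-test into one.

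**Conclusion.** The concern holds: a stated diagnostic objective, with screening as its goal, has no planned analysis that estimates diagnostic accuracy. At the planned group sizes a significant result is compatible with an AUC of about 0.60, and a difference found with 90% power with about 0.67. These figures rest on a two-sided 5% test, normal distributions with equal variance, and 33 patients against 167 to 177.

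The conclusion goes no further. The documents do not show that a weak marker will be called diagnostic, that phase angle is weak, or that its independent association goes untested. This should be put right before analysis, and it can be done with data the plan already collects.

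**What to change.** Add a diagnostic-accuracy section to the analysis plan.

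- Name whole-body phase angle as the single marker and report its AUC with 95% interval for sarcopenic obesity.
- Compare the AUC of age + sex with that of age + sex + phase angle, with bootstrap optimism correction.
- At any cut-off, state how it is chosen. Report sensitivity, specificity and predictive values with exact intervals, and optimism-corrected values alongside. As an illustration of why, in 4,000 simulations at d = 0.6 a cut-off chosen on the same data showed a mean Youden index of 0.31, while the selected cut-offs truly achieved 0.22.
- Label sex-specific cut-offs and segmental phase angles exploratory.
- Keep the measures that define the label (skeletal muscle index, body fat, BMI, waist circumference, grip strength, gait speed) out of the diagnostic model.
- State as a limitation that skeletal muscle index in the label and phase angle come from the same device, so accuracy may be inflated.
- Base any diagnostic or screening statement on these estimates, not on the t-test p-value.

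The cost is wording and routine computation, with no new patients or visits. The downside is less flattering results: the pooled AUC carries about ±0.10, sex-specific estimates are much wider because they split about 33 cases, and corrected accuracy will look worse than uncorrected.

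### Exclusion (5) and the follow-up-data part of exclusion (2) define the cohort by events after enrolment; followed as written, with deaths counted as events, they overstate 2-year mortality and can distort group comparisons

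*Combined protocol and SAP*

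**What the plan says.** Two entries in the protocol's Exclusion Criteria depend on what happens after enrolment. Item 5 is "Voluntary withdrawal for any reason, including loss to follow-up". Item 2 reads "Incomplete clinical or follow-up data or unwillingness/inability to undergo regular follow-up"; its last part can be judged at entry, but completeness of follow-up data cannot. Inclusion (3) already asks for "willingness to adhere to follow-up arrangements", so item 5 is not needed as a baseline screen.

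Under Follow-up Endpoints, the primary endpoint is "Changes in pulmonary function, dyspnea scores, and body composition at 2 years" and the secondary is "Acute exacerbations, hospitalizations, or death within 2 years", with "Follow-ups at 6, 12, and 24 months". The prognostic analysis compares patients with sarcopenic obesity against patients free of sarcopenia at entry on hospital stay, readmission and mortality, by Kaplan-Meier and log-rank. The available text states no analysis population, censoring rule, missing-data method or expected loss rate.

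**The concern.** A prognostic cohort should be fixed at baseline. Here, taken literally, a patient who enrols, attends at 6 and 12 months and is then lost was never eligible, and drops out of both the survival comparison and the 2-year change analysis. The sample is then selected on the course of follow-up.

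For mortality, the patients removed are all alive when lost, while those who died under observation stay, so the death rate among those retained is too high. If one group loses more patients than the other, or if sicker patients are more likely to be lost, the comparison between groups can shift too. In frail COPD patients over 65 neither can be ruled out.

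**Working it through.** **Inputs.** The documents give no event risk and no loss rate, so every rate below is an assumption. The planned sample size cannot be re-run, because no effect size, standard deviation or within-patient correlation is stated; nothing below depends on it except the cell sizes used for the log-rank error rates.

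**1. Mortality, loss independent of death, lost patients deleted.** Take constant hazards over 2 years, with *p* the true risk and *l* the loss probability in the absence of death.
- a = −ln(1 − p), b = −ln(1 − l), s = exp(−(a + b))
- observed deaths = a/(a + b) × (1 − s); lost = b/(a + b) × (1 − s)
- apparent risk = deaths / (1 − lost)

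For p = 0.20 and l = 0.20: a = b = 0.2231 and s = 0.64, so deaths = lost = 0.5 × 0.36 = 0.18. Apparent risk = 0.18/0.82 = 0.2195.

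| True 2-year mortality | 10% loss | 20% loss | 30% loss |
|---|---|---|---|
| 10% | 10.5% | 11.1% | 11.8% |
| 20% | 20.9% | 22.0% | 23.2% |
| 30% | 31.2% | 32.6% | 34.2% |

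In simulation with a true 15%, keeping everyone and censoring at loss returned 15.0% at 10, 20 and 30% loss.

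**2. Group contrast for mortality.** The ratio of cumulative hazards is ln(1 − r1)/ln(1 − r2), where r1 and r2 are the apparent risks. With equal true risk of 15, 20 or 30%:
- equal loss: 1.00
- 20% vs 10% loss: 1.059, 1.057, 1.055
- 30% vs 10%: 1.130, 1.127, 1.121
- 10% vs 30%: 0.885, 0.887, 0.892

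With true risks of 20% vs 10% (hazard ratio 2.118), equal loss of 10 to 30% gives 2.114 to 2.102, which is trivial; 10% vs 30% loss gives 1.87. Log-rank type I error at 33 vs 144 patients (72 + 72 for the comparison group) is 7.0 to 7.5% at 30% vs 10% loss and 4.5 to 5.4% at 10% vs 30%. The second range does not mean absence of bias: on the log scale the spurious ratio is just as large.

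**3. Non-fatal events.** Item 5 makes no exception for a patient who has an event and is lost later. If that patient is deleted too, retention depends only on loss and death. When these are independent of the non-fatal event, its Kaplan-Meier risk is unchanged: a true 30% stayed at 30.0% in simulation, at 10 or 30% loss and with no deaths or 15% deaths. The crude proportion dips slightly, from 46.6% to 46.1% at 20% loss with 15% deaths. If only loss before the event leads to exclusion, the same 46.6% reads 49.2%.

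**4. Early deaths.** If a death before 24 months were treated as incomplete follow-up data, deaths themselves would be deleted and mortality understated.

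**5. Primary 2-year changes.** Independent loss causes no bias. Suppose instead that changes have SD 1 at each visit, visit correlation is 0.5 to 0.7, and the odds of dropout rise 2- to 3-fold per SD of worsening at the last visit. With no true group difference, deletion gives a spurious 24-month difference of 0.03 to 0.07 SD at 20% vs 10% loss and 0.07 to 0.14 SD at 30% vs 10%; a likelihood model using all visits gives about 0.00. If dropout depends on the value not yet seen, both are biased at 30% vs 10%: 0.10 to 0.17 SD with deletion and 0.05 to 0.10 SD with the model.

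**6. Informative loss for mortality.** With a gamma frailty shared by death and loss, equal true risk of 20 to 30% and 30% vs 10% loss, the hazard ratio at frailty variance 0.5, 1 and 2 is 0.94, 0.90 and 0.81 to 0.84 with censoring, and 1.05 to 1.06, 1.00 and 0.91 to 0.93 with deletion. Neither approach is reliable.

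**The case against.** The strongest reply is that item 5 is a withdrawal rule put under the wrong heading. Kaplan-Meier is normally chosen because it handles censoring, which suggests the authors meant to censor. That is plausible, but the text does not say so, and a withdrawal rule would still need to state how those patients are analysed.

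A reader might infer that the rule overstates every 2-year event risk. The documents do not support that: step 3 shows no Kaplan-Meier bias for exacerbation or hospitalization under the literal wording and independent loss. Nor is the direction for mortality assured if early deaths count as incomplete data, or if loss is related to frailty.

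A reader might also infer that power falls below the planned 90%. The plan, "Using PASS 15.0 for repeated-measures ANOVA", says "the study requires 200 participants" without saying whether these are enrolled or evaluable. If evaluable, power need not fall. (The listed cells sum to 33 + 33 + 72 + 72 = 210, a separate matter.)

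Finally, censoring is not a cure. In step 6 it was no better than deletion at frailty variance 0.5 and worse at 1 and 2. This stands, and is why the fix includes a sensitivity analysis. Participation is also voluntary, so a patient may withdraw permission for use of data; the fix allows for that.

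**Conclusion.** The point holds, in limited form. Events known only after enrolment are used to define the cohort, and nothing in the available text keeps the affected patients. With deaths counted as events and loss independent of outcome, 2-year mortality is overstated by about 0.5 to 4 percentage points for true risks of 10 to 30% and losses of 10 to 30%. The mortality contrast is essentially unaffected by equal loss, and moves by a factor of about 1.12 to 1.13, or 0.885 to 0.892 the other way, at 30% vs 10%. Non-fatal events are biased upward only if loss before the event alone leads to exclusion. The primary changes are at risk only if dropout is related to worsening, but collected 6- and 12-month data are discarded in any case. The effect is modest and rests on assumed rates; the drafting fault does not. It should be fixed.

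**What to change.** - Delete exclusion (5), and the words 'or follow-up' before 'data' in exclusion (2), keeping the conditions that can be judged at baseline. If (5) was meant as a withdrawal rule, move it to a withdrawal section.
- Analyse all eligible enrolled patients with a baseline assessment, using data collected up to withdrawal unless the patient withdraws permission for its use.
- In the survival analyses, censor withdrawn or lost patients at last contact. State that death before 24 months is a mortality event, and state how death is handled for readmission.
- Analyse the 2-year changes with a longitudinal model using all available visits, and report deaths alongside.
- Report loss by group and add one sensitivity analysis for informative loss.

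The cost is one extra model, one sensitivity analysis and reported completeness that will look less favourable. No extra patients or procedures are needed.

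### No planned analysis of lung function, dyspnea or inflammatory markers adjusts for medication or any other confounder, so treatment and severity differences could be read as effects of sarcopenic obesity

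*Combined protocol and SAP*

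**What the plan says.** Data Collection lists, under clinical records, "physical performance (SPPB), medication use, pulmonary function tests, COPD exacerbations in the past year". It names no drug classes and no timing. Follow-up Endpoints sets the primary endpoint as "Primary: Changes in pulmonary function, dyspnea scores, and body composition at 2 years", with visits at 6, 12 and 24 months, but does not say what is recorded at each visit. The laboratory panel includes CRP, IL-6, TNF-alpha, HbA1c and cholesterol, and Research Objectives sets out to "reveal the effects of inflammation and metabolic disorders in sarcopenic obesity".

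The analysis text has three parts:

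- A comparison of clinical data by sarcopenic-obesity status: "Differences between groups were analyzed using Student's t-test for continuous variables and the chi-square test for categorical variables".
- Univariate and multivariate logistic regression for factors associated with sarcopenic obesity.
- Kaplan-Meier curves and a log-rank test for hospital stay, readmission and mortality, with no covariates.

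The bronchodilator state of spirometry is given only in Inclusion Criterion 4 ("with a post-bronchodilator FEV1/FVC ratio < 0.70"), not for the primary endpoint.

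**The concern.** Patients are classified by body composition, not randomised, and the protocol does not fix their background treatment. Medication can plausibly act on both sides of the comparison: on muscle and fat, which define the groups, and on lung function, dyspnea and blood markers, which are compared between them. These pathways are assumed here as general clinical knowledge; the documents do not describe them. Age, smoking, comorbidity and disease severity raise the same problem.

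An unadjusted test cannot separate such differences from an effect of sarcopenic obesity. For baseline variables this can be repaired later if the data exist. Treatment changes during follow-up that were never recorded cannot be reliably reconstructed. Serial spirometry taken in varying bronchodilator states likewise cannot be put right at analysis.

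**Working it through.** **1. Which analysis adjusts which outcome.** Setting the analysis sections against the endpoints:

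- Lung function: named in the group comparison, by an unadjusted test. It could also enter the logistic model, but there as a predictor.
- Dyspnea: no comparison is named, although the open list of clinical data could cover it.
- CRP, IL-6 and TNF-alpha: no comparison is named, with the same caveat.
- Medication: not named in any analysis. It could be tabulated by group or enter the logistic model as a clinical variable.
- The repeated-measures ANOVA used for the sample size does not reappear in the analysis text.

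No model has any of these outcomes on the left-hand side with a covariate on the right.

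**2. The plan's own figure.** Sample Size Calculation says "the study requires 200 participants (33 sarcopenic obese, 33 non-obese sarcopenic, 72 obese non-sarcopenic, and 72 non-obese non-sarcopenic". The listed groups give 33 + 33 + 72 + 72 = 210, not 200. The total cannot be derived, because no effect size, SD or within-subject correlation is stated. The figure matters here only for the group sizes: 33 sarcopenic-obese patients against 33 + 72 + 72 = 177 without sarcopenic obesity, or 72 + 72 = 144 without sarcopenia.

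**3. What these groups can detect.** Two-sided 5%, 90% power, normal approximation, in SD units:

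MDE = (1.960 + 1.282) × √(1/n1 + 1/n2)

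- 33 vs 177: 3.242 × 0.1896 = 0.615
- 33 vs 144: 3.242 × 0.1930 = 0.626

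**4. Size of a spurious difference (illustration).** The documents give no medication frequency by group and no medication effect, so both are assumed: a difference in use, Δp, of 10 to 40 points and an effect, e, of 0.2 to 0.5 SD. Bias b = Δp × e. With SE = √(1/33 + 1/177) = 0.1896, the probability of rejecting a true null is 1 − Φ(1.96 − b/SE) + Φ(−1.96 − b/SE).

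| Δp | e (SD) | b (SD) | Rejection under the null |
|---|---|---|---|
| 0.10 | 0.2 | 0.02 | 5.1% |
| 0.20 | 0.3 | 0.06 | 6.2% |
| 0.20 | 0.5 | 0.10 | 8.2% |
| 0.30 | 0.5 | 0.15 | 12.4% |
| 0.40 | 0.5 | 0.20 | 18.4% |

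The largest bias is about a third of the detectable difference (0.20 / 0.615 = 0.33).

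**5. Spirometry (illustration).** Suppose follow-up spirometry were pre-dose, the groups differed by 10 to 30 points in starting or stepping up maintenance bronchodilators, and this raised FEV1 by 50 to 150 mL. The spurious difference in change would be 0.10 × 50 = 5 mL to 0.30 × 150 = 45 mL. All three inputs are assumptions. No SD is given against which to judge the result.

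**The case against.** Much can be said for the plan:

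- **Medication is not shut out.** The list of compared clinical data is open, the chi-square test would cover a categorical medication variable, and the logistic model draws on unlisted clinical variables. A reader might infer that medication enters no comparison at all; the text does not support that. The narrower point stands, because neither route adjusts an outcome.
- **The t-test is not assigned to the endpoints.** It sits under a descriptive heading and is not tied to 2-year change, dyspnea or inflammation. This is correct. For dyspnea and the markers, the first need is a named analysis.
- **Timing is not stated.** A reader might infer that medication is recorded only at entry. The same list holds lung function and mMRC, which must be repeated because their change is the endpoint. The consent form, which may describe visits, was not available for this check. What stands is that the protocol sections do not specify an update.
- **Medication is one confounder among several.** Inhaler class partly follows severity, so adjusting for drugs alone would not separate disease from treatment. This stands and shapes the fix.
- **Adjustment can add bias.** Glucose- and lipid-lowering drugs are prescribed because of HbA1c and cholesterol, and treatment changes after baseline may lie on the causal path. Both warnings stand.
- **The aim is partly predictive.** Treatment confounding matters less for a prognostic model, but the objective on inflammation and metabolism is explanatory.

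**Conclusion.** The point holds in limited form. Medication is collected, but no specified analysis of lung function, dyspnea or inflammatory markers adjusts for it or for any other confounder. Differences in treatment and severity could therefore be read as effects of sarcopenic obesity.

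The stronger statement, that they will be so read or that the study cannot tell the two apart, is not supported: neither the imbalance nor the medication effect is known. Under the assumed ranges the consequence runs from negligible (0.02 SD, 5.1% false positives) to material (0.20 SD, 18.4%). The sponsor should act before follow-up visits begin, since the medication and spirometry records depend on what is done at those visits.

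**What to change.** 1. **Adjusted outcome model.** For 2-year change in lung function and dyspnea, and for the inflammatory markers, prespecify linear regression (ANCOVA or a mixed model) on group in place of an unadjusted test. Include the baseline value where change is analysed, plus a short fixed set of baseline covariates: age, sex, smoking, Charlson index, systemic corticosteroid use and maintenance inhaler class. The last two require the medication record to define drug classes. Keep the set small, because only about 33 sarcopenic-obese patients are expected.
2. **One bronchodilator state.** Measure lung function post-bronchodilator at baseline and every visit, the state already required for eligibility.
3. **Medication update.** Re-record medication at the existing 6-, 12- and 24-month contacts and tabulate it by group. Use changes after baseline only in a sensitivity analysis.
4. **HbA1c and cholesterol.** Do not enter glucose- or lipid-lowering drugs as simple covariates; report these markers by treatment status.

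Cost: slightly wider intervals, a few minutes per contact for the medication update, and some extra time per visit if spirometry was not already planned as post-bronchodilator. Groups, visits and endpoints stay as they are.
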